9.3 SITE INSPECTIONS

Site visits will be conducted by the Sponsor or an authorized representative for inspection of study data, patients' medical records, and eCRFs. The investigator will permit national and local health authorities; Sponsor monitors, representatives, and collaborators; and the IRBs/ECs to inspect facilities and records relevant to this study.

9.4 ADMINISTRATIVE STRUCTURE

This research study is being sponsored globally by F. Hoffmann-La Roche Ltd of Basel, Switzerland and may be implemented in individual countries by Roche's local affiliates. The Sponsor will perform project management, study management, monitoring, vendor management, and statistical programming. An IxRS will be used for patient randomization and for management of study drug requests and shipments.

A central laboratory will be used for most laboratory assessments and for storage of other laboratory samples (i.e., anti-lampalizumab antibody serum samples) prior to being shipped to Sponsor or its designee for analysis. Data will be recorded by an EDC system using eCRFs (see Section 7.1) or forwarded to Sponsor electronically. A central reading center will be used for ocular imaging analyses (i.e., FAF, NI, CFP, FA, and SD-OCT) and microperimetry data, which will be forwarded to the Sponsor electronically.

9.5 PUBLICATION OF DATA AND PROTECTION OF TRADE SECRETS

Regardless of the outcome of a trial, the Sponsor is dedicated to openly providing information on the trial to healthcare professionals and to the public, both at scientific congresses and in peer-reviewed journals. The Sponsor will comply with all requirements for publication of study results. For more information, refer to the Roche Global Policy on Sharing of Clinical Trials Data at the following Web site:

<http://www.rochetrials.com/pdf/RocheGlobalDataSharingPolicy.pdf>

The results of this study may be published or presented at scientific congresses. For all clinical trials in patients involving an IMP for which a marketing authorization application has been filed or approved in any country, the Sponsor aims to submit a journal manuscript reporting primary clinical trial results within 6 months after the availability of the respective clinical study report. In addition, for all clinical trials in patients involving an IMP for which a marketing authorization application has been filed or approved in any country, the Sponsor aims to publish results from analyses of additional endpoints and exploratory data that are clinically meaningful and statistically sound.

The investigator must agree to submit all manuscripts or abstracts to the Sponsor prior to submission for publication or presentation. This allows the Sponsor to protect

proprietary information and to provide comments based on information from other studies that may not yet be available to the investigator.

In accordance with standard editorial and ethical practice, the Sponsor will generally support publication of multicenter trials only in their entirety and not as individual center data. In this case, a coordinating investigator will be designated by mutual agreement.

Authorship will be determined by mutual agreement and in line with International Committee of Medical Journal Editors' authorship requirements. Any formal publication of the study in which contribution of Sponsor personnel exceeded that of conventional monitoring will be considered as a joint publication by the investigator and the appropriate Sponsor personnel.

Any inventions and resulting patents, improvements, and/or know-how originating from the use of data from this study will become and remain the exclusive and unburdened property of the Sponsor, except where agreed otherwise.

9.6 PROTOCOL AMENDMENTS

Any protocol amendments will be prepared by the Sponsor. Protocol amendments will be submitted to the IRB/EC and to regulatory authorities in accordance with local regulatory requirements.

Approval must be obtained from the IRB/EC and regulatory authorities (as locally required) before implementation of any changes, except for changes necessary to eliminate an immediate hazard to patients or changes that involve logistical or administrative aspects only (e.g., change in Medical Monitor or contact information).

Appendix 1 Schedule of Assessments

Table 1 Study Flowchart for Q4W Arm: Day 1, Week 4 through Week 52, and Early Termination

Assessment Window (Days)	Day 1 ^a		Week													ET ^b
	Data Extracted from Parent Study	Data Obtained at Day 1 Visit	4	8	12	16	20	24	28	32	36	40	44	48	52	≥30
			±5	±5	±5	±5	±5	±5	±5	±5	±5	±5	±5	±5	±5	
Written informed consent		x ^c														
Review of inclusion and exclusion criteria		x														
Demographic information (age, sex, and self-reported race/ethnicity) ^d	x															
NEI VFQ-25 ^e (as applicable)	x							x						x		x
FRI Index ^e (as applicable)	x							x						x		x
Vital signs ^f																x
Central laboratory samples (hematology, coagulation, chemistry panel, and urinalysis) ^g																x
Biomarker plasma sample ^g		x														
Urine pregnancy test ^{g,h}		x	x	x	x	x	x	x	x	x	x	x	x	x	x	
Serum ATA sample ^g	x													x		x

Appendix 1 Schedule of Assessments (cont.)

Table 1 Study Flowchart for Q4W Arm: Day 1, Week 4 through Week 52, and Early Termination (cont.)

Assessment Window(Days)	Day 1 ^a		Week													ET ^b
	Data Extracted from Parent Study	Data Obtained at Day 1 Visit	4	8	12	16	20	24	28	32	36	40	44	48	52	≥30
			±5	±5	±5	±5	±5	±5	±5	±5	±5	±5	±5	±5	±5	
Serum PK sample for lampalizumab concentration ^g	x													x		x
Optional aqueous sample ^{g, i}														x		
BCVA testing (starting at 4 m) ^j	x		x	x	x	x	x	x	x	x	x	x	x	x	x	x
LL BCVA testing (starting at 4 m) ^j	x		x		x									x		x
MNRead or Radner Reading Charts ^{j, k} (as applicable)	x													x		x
Pretreatment IOP measurement ^j	x		x	x	x	x	x	x	x	x	x	x	x	x	x	x
Mesopic microperimetry at selected sites (study eye only) ^l	x													x		x
Slit lamp examination	x		x	x	x	x	x	x	x	x	x	x	x	x	x	x
Dilated binocular indirect ophthalmoscopy	x		x	x	x	x	x	x	x	x	x	x	x	x	x	x
FAF ^m	x							x			x			x		x
SD-OCT ^m	x							x						x		x
Near-infrared imaging ^m	x							x			x			x		x

Appendix 1 Schedule of Assessments (cont.)

Table 1 Study Flowchart for Q4W Arm: Day 1, Week 4 through Week 52, and Early Termination (cont.)

Assessment Window(Days)	Day 1 ^a		Week													ET ^b
	Data Extracted from Parent Study	Data Obtained at Day 1 Visit	4	8	12	16	20	24	28	32	36	40	44	48	52	≥30
			±5	±5	±5	±5	±5	±5	±5	±5	±5	±5	±5	±5	±5	
Color fundus photography ^m	x													x		x
Fluorescein angiography ^m	x															x
Administration of larpalizumab injection to study eye		x	x	x	x	x	x	x	x	x	x	x	x	x	x	
Post-treatment finger-counting and IOP measurement ⁿ		x	x	x	x	x	x	x	x	x	x	x	x	x	x	
Concomitant medications ^o	x	x	x	x	x	x	x	x	x	x	x	x	x	x	x	x
Adverse events ^p	x	x	x	x	x	x	x	x	x	x	x	x	x	x	x	x
Concurrent ocular procedures ^q		x	x	x	x	x	x	x	x	x	x	x	x	x	x	x
Follow-up call ^r		x	x	x	x	x	x	x	x	x	x	x	x	x	x	

ATA= anti-therapeutic antibody; BCVA= best corrected visual acuity; eCRF =electronic Case Report Form; ET=early termination; FAF=fundus autofluorescence; FRI= Functional Reading Independence; ICF= informed consent form; IOP= intraocular pressure; LL BCVA= low-luminance BCVA; MNRead= Minnesota Low-Vision Reading Test; NEI VFQ-25= National Eye Institute Visual Functioning Questionnaire 25-Item Version; OLE= open-label extension; PK= pharmacokinetic; Q4W= every 4 weeks; SD-OCT= spectral domain-optical coherence tomography; VA= visual acuity.

Note: All ocular assessments are to be performed for both eyes unless noted otherwise. All assessments are to be performed on the same day except for study laboratory sample collections, which can be collected up to 7 days before or after scheduled visit. *The study drug injection may be delayed for reasons specified in the Section 3.1.1.* All study visits will be scheduled relative to date of Day 1 visit.

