2.3 PHARMACOKINETIC OBJECTIVES

The pharmacokinetic (PK) objective for this study is to observe the systemic trough concentrations of 10 mg lampalizumab administered by *intravitreal* injections through the analysis of the serum lampalizumab concentrations.

The exploratory PK objectives for this study are to observe the aqueous humor concentrations of lampalizumab and to explore possible relationships between lampalizumab PK, biomarkers, and clinically related endpoints.

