3.3.2 Rationale for Biomarker Assessments

A biomarker plasma sample will be collected at the Day 1 visit of the study. This sample will allow comparison of plasma biomarkers of the complement-pathway between the baseline sample collected in the parent study and a sample collected 2 years later (at entry into Study GX30191). Evaluation of the longitudinal stability of plasma biomarkers will aid the understanding of relationships between these biomarkers and other biomarkers and endpoints in the study.

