4.5.5 Laboratory and Other Biological Samples

At the scheduled visit, specimens should be collected prior to study eye treatment and FA assessments (if applicable). Fasting is not required prior to specimen collection. Specimens will be forwarded to the central laboratory, where they will be analyzed or forwarded to the Sponsor or its designee for analysis and/or storage.

The following assessments will be performed:

- Urine pregnancy test (performed at the site) prior to each study treatment for women of childbearing potential, including those who have had tubal ligation
 - If positive, collect blood sample for the serum pregnancy test and forward to central lab for analysis. If the serum pregnancy test is positive, discontinue the patient from study treatment.
- Measurement of anti-lampalizumab antibodies in serum samples
- Measurement of lampalizumab concentration in serum samples
- Measurement of lampalizumab and CFD levels in optional anterior chamber (aqueous humor) paracentesis samples in order to assess PK and pharmacodynamic (PD) relationships
- Assessment of measures of the complement pathway in plasma samples

The following assessments will be performed only at the early termination visit:

- Urinalysis: specific gravity, pH, blood, protein, ketones, glucose, bilirubin, urobilinogen, and microscopic examination (if any of the preceding urinalysis tests, other than glucose and ketones, are abnormal)

- Hematology: hemoglobin, hematocrit, quantitative platelet count, red blood cell counts, white blood cell counts, and differentials, including neutrophils, bands, lymphocytes, basophils, eosinophils, and monocytes (absolute)
- Chemistry panel (serum or plasma): sodium, potassium, chloride, bicarbonate, glucose, blood urea nitrogen, creatinine, calcium, phosphorus, total and direct bilirubin, total protein, albumin, aspartate aminotransferase (AST), alanine aminotransferase (ALT), lactate dehydrogenase, alkaline phosphatase, and uric acid
- Coagulation: activated partial thromboplastin time and prothrombin time

The samples (except those for hematology, serum chemistry, urinalysis, coagulation, and serum and urine pregnancy tests that will be destroyed after their analysis during the study) will be stored for up to 5 years after the date of final closure of the associated clinical database.

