6.5 PHARMACOKINETIC ANALYSES

The PK analyses will include all enrolled patients who have *received at least one dose of study drug and have at least one serum sample. The analyses will be summarized by treatment group in the parent study.* Serum concentrations of lampalizumab will be summarized descriptively.

Concentrations of lampalizumab from the optional collection of aqueous humor may be reported and/or summarized as appropriate. Additional PK/PD and exposure–response analyses may be conducted as appropriate. Population PK modeling may be performed to characterize inter-individual variability, which may be reported separately from the Clinical Study Report.

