Appendix 1 Schedule of Assessments (cont.)

Table 1 Study Flowchart for Q4W Arm: Day 1, Week 4 through Week 52, and Early Termination (cont.)

- ^a The Day 1 visit will be performed on the same day as the Week 96 visit in the parent study. *If a site is not able to collect images at the Week 96 visit of the parent study, the Day 1 visit study treatment will be interrupted and the images will be collected as soon as possible and prior to study treatment administration at the next study treatment visit (e.g., Week 4 or Week 6). The reason for study treatment interruption at Day 1 visit will be recorded on the study treatment interruption eCRF.*
- ^b For patients who discontinue from the study, early termination assessments will be performed after a minimum of 30 days has elapsed following the last study drug treatment.
- ^c At the sites where investigator intends to ask his patients to self-administer antimicrobials pre and post injection, the ICF needs to be signed at an earlier date (e.g., Week 90 or 92 visit in parent study) in order to allow the ICF to be in place prior to the patient receiving pre-injection antimicrobials. In addition, during the Week 96 visit, if the ICF is signed prior to completion of the Week 96 assessments of the parent study, then the Week 96 parent study blood draws and the Day 1 OLE blood draw can be performed at the same time.
- ^d The sites will transcribe demographics data from the parent study to OLE RAVE eCRF.
- ^e To be administered by the site staff (except for the VA examiner) prior to any other visit assessments being performed on that day.
- ^f Vital signs include measurements of temperature, respiratory rate, pulse rate, and systolic and diastolic blood pressure while the patient is in a seated position after resting for 5 minutes.
- ^g If laboratory sample is being obtained on study visit day, it must be obtained prior to fluorescein angiography (if applicable) and prior to study drug treatment.
- ^h Starting on Day 1, collect and perform the urine pregnancy test for women of childbearing potential, including those who have had tubal ligation, at each study drug treatment visit. If positive, collect the serum pregnancy sample and forward to central laboratory for testing, do not administer study drug, and if positive, withdraw the patient from the study.
- ⁱ Optional aqueous sample will be collected from the patients who consented to it.
- ^j Perform prior to dilating the eyes.

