Appendix 1 Schedule of Assessments (cont.)

Table 2 Study Flowchart for Q4W Arm: Week 56 through Week 96 and Early Termination (cont.)

- ^b This study may potentially extend beyond Week 96. *The sites will be informed in timely manner.*
- ^c To be administered by the site staff (except for the VA examiner) prior to any other visit assessments being performed on that day.
- ^d If laboratory sample is being obtained on study visit day, it must be obtain prior to fluorescein angiography (if applicable) and prior to study drug treatment.
- ^e Starting on Day 1, collect and perform the urine pregnancy test for women of childbearing potential, including those who have had tubal ligation, at each study drug treatment visit. If positive, collect the serum pregnancy sample and forward to central laboratory for testing, do not administer study drug, and if positive withdraw the patient from the study.
- ^f Optional aqueous sample will be collected from the patients who consented to it.
- ^g Perform prior to dilating the eyes.
- ^h Either MNRead charts or Radner Reading Charts will be performed during the study visit prior to dilating the eyes (see the tables in [Appendix 14](#) and [Appendix 15](#), respectively, for which chart to use according to country of the site). The test will be administered first monocularly (right/left eye) and then binocularly (both eyes).
- ⁱ To be performed post-dilation on the study eye only; the data will be forwarded to the central reading center.
- ^j Performed for both eyes; and results will be forwarded to the central reading center. See the center reading center manual. If a patient misses a study visit when ocular images are scheduled to be obtained, the images should be obtained at the next scheduled visit.

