Appendix 1 Schedule of Assessments (cont.)

Table 3 Study Flowchart for Q6W Arm: Day 1, Week 6 through Week 96, and Early Termination (cont.)

Note: All ocular assessments are to be performed for both eyes unless noted otherwise. All assessments are to be performed on the same day except for study laboratory sample collection, which can be collected up to 7 days before or after scheduled visit. *The study drug injection may be delayed for reasons specified in Section 3.1.1.* All study visits will be scheduled relative to the Day 1 visit date.

- ^a Day 1 visit will be performed on the same day as Week 96 visit in parent study. *If a site is not able to collect images at parent study Week 96 visit then Day 1 visit study treatment will be interrupted and the images will be collected as soon as possible and prior to study treatment administration at the next study treatment visit (e.g. Week 4 or Week 6). The reason for study treatment interruption at Day 1 visit will be recorded on the study treatment interruption eCRF.*
- ^b For patients who discontinue early from the study, early termination assessments will be performed after a minimum of 30 days has elapsed following the last study drug treatment.
- ^c This study may potentially extend beyond *the Week 96 visit. The sites will be informed in timely manner.*
- ^d At the sites where investigator intends to ask his patients to self-administer antimicrobials pre and post injection, the ICF needs to be signed at an earlier date (e.g., Week 90 or 92 visit in parent study) in order to allow the ICF to be in place prior to the patient receiving pre-injection antimicrobials. In addition, during the Week 96 visit, if the ICF is signed prior to completion of the Week 96 assessments of the parent study, then the Week 96 parent study blood draws and the Day 1 OLE blood draw can be performed at the same time.
- ^e The sites will transcribe demographics data from the parent study to OLE RAVE eCRF.
- ^f To be administered by the site staff (except for the VA examiner) prior to any other visit assessments being performed on that day.
- ^g Vital signs include measurements of temperature, respiratory rate, pulse rate, and systolic and diastolic blood pressure while the patient is in a seated position after resting for 5 minutes.
- ^h If laboratory sample is being obtained on study visit day, it must be obtain prior to fluorescein angiography (if applicable) and prior to study drug treatment.

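### Appendix 1 lets serum PK be drawn up to 7 days after an injection visit, so post-dose samples can enter a summary meant to describe trough

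*Combined protocol and SAP*

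**What the plan says.** - **Objective.** Section 2.3 sets the non-exploratory PK aim as "to observe the systemic trough concentrations of 10 mg lampalizumab" from serum samples. The synopsis says the same.
- **Schedule.** Apart from early termination, extension-study serum PK is drawn at Weeks 48 and 96 in both arms (Appendix 1, Tables 1 to 3). An injection is scheduled at each of those visits. The Day 1 PK value is taken over from the parent study.
- **Sampling window.** All assessments are same-day except, in the Table 1 note (Q4W), "study laboratory sample collections, which can be collected up to 7 days before or after scheduled visit" and, in the Table 3 note (Q6W), "study laboratory sample collection, which can be collected up to 7 days before or after scheduled visit". Table 2 (Q4W, Weeks 56 to 96) has no such sentence.
- **Pre-dose rule.** The serum PK row carries the laboratory-sample footnote. In Table 1 (footnote g) it begins "If laboratory sample is being obtained on study visit day, it must be obtained prior to fluorescein angiography" and goes on to require collection before study drug. Table 2 footnote d and Table 3 footnote h have the same condition: "If laboratory sample is being obtained on study visit day, it must be obtain prior to fluorescein angiography". Section 4.5.5 reads "At the scheduled visit, specimens should be collected prior to study eye treatment and FA assessments (if applicable".
- **Analysis.** Section 6.5 includes all enrolled patients who have "received at least one dose of study drug and have at least one serum sample" and summarizes concentrations descriptively, without naming a statistic.
- **Biomarker plasma.** Section 3.3.2 compares the parent-study baseline with "a sample collected 2 years later (at entry into Study GX30191". The Day 1 plasma row carries the same laboratory footnote.

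**The concern.** A trough is the level just before the next injection. If the visit's injection goes ahead as scheduled, a sample taken 1 to 7 days after the visit is an early post-dose sample. Nothing in the schedule forbids such a sample, and nothing in Section 6.5 would flag or exclude it. If serum concentration is falling from day 7 onward, a day-7 draw pushes the reported trough upward whatever the half-life. Each patient has only two scheduled on-treatment serum PK samples through Week 96, so one late draw is half of that patient's on-treatment data. The same values feed the planned descriptive comparison of PK by anti-drug antibody status in Section 6.6.

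A second, smaller issue follows from the same window. The Day 1 biomarker plasma could be drawn after a prior-sham patient's first active injection. It would then no longer be a drug-free entry sample for the 2-year stability comparison. The size of that effect is unknown.

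**Working it through.** The plan states no figure on this point, so there is nothing to reproduce. The check is a reading of the schedule followed by an illustration under stated assumptions.

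**1. Which samples are exposed**

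| Sample | Injection at visit | 7-day note | Pre-dose rule | Late draw permitted |
|---|---|---|---|---|
| Q4W Week 48 (Table 1) | yes | yes | visit day only | expressly |
| Q4W Week 96 (Table 2) | yes | no | visit day only | by implication only |
| Q6W Weeks 48, 96 (Table 3) | yes | yes | visit day only | expressly |
| Early termination | no | not relevant | – | not affected (at least 30 days after last dose) |

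Section 4.5.5 does not close the gap, because it too speaks of collection at the scheduled visit.

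**2. Where a late draw falls in the dosing interval**

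Dosing intervals are 28 and 42 days (Section 3.1.1). A draw 1 to 7 days after injection lies at 1/28 to 7/28 = 3.6% to 25% of the Q4W interval and at 1/42 to 7/42 = 2.4% to 16.7% of the Q6W interval.

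**3. How far a day-7 level is from trough**

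Assume mono-exponential decline in serum with apparent half-life t (not in the documents; 4 to 14 days taken as a range). Then the ratio R = 2^((28−7)/t) for Q4W and 2^((42−7)/t) for Q6W.

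**4. Effect on the summary**

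Let a fraction f of samples be drawn at day 7 and the rest at trough. The arithmetic mean is multiplied by 1 − f + f·R and the geometric mean by R^f. With f = 0.05 (assumed):

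| t (days) | R, Q4W | R, Q6W | Arithmetic, Q4W | Arithmetic, Q6W | Geometric, Q4W | Geometric, Q6W |
|---|---|---|---|---|---|---|
| 4 | 38.05 | 430.54 | 2.85 | 22.48 | 1.20 | 1.35 |
| 6 | 11.31 | 57.02 | 1.52 | 3.80 | 1.13 | 1.22 |
| 14 | 2.83 | 5.66 | 1.09 | 1.23 | 1.05 | 1.09 |

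For example, at t = 4 in Q4W: 0.95 + 0.05 × 38.05 = 2.85, and 38.05^0.05 = 1.20. With 5% late draws a median barely moves.

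**5. The early side of the window**

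A draw 7 days before the visit falls at nominal day 21 or 35. Relative to trough it is 2^(7/t), which is 3.36 at t = 4 and 1.41 at t = 14. With the ±5-day visit windows and the 22-day minimum between injections, the shortest interval is 22 days for Q4W (the larger of 22 and 28 − 10) and 32 days for Q6W (42 − 10). The earliest such draw is then day 22 − 7 = 15 or day 32 − 7 = 25. Pre-dose samples therefore also need actual time since dose.

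**The case against.** The strongest reply is that the intent is plainly pre-dose: Section 4.5.5 and the footnotes say so for visit-day draws, and the 7-day sentence is a general allowance for all laboratory samples. That is fair as to intent, but the allowance is express and covers the serum PK row as written. Appendix 16 shows how an unconditional rule looks, since aqueous samples must be taken before treatment whatever the day.

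Appendix 16 also refers sites to a Central Laboratory Manual, which is not among the documents and may be stricter. It would still have to be reconciled with the protocol's permission. The same holds for the Data Analysis Plan. Population PK modeling could use actual sampling times, but Section 6.5 makes it optional, and the planned summary has no such adjustment.

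Several limits stand:
- The half-life, the late-draw share and the decay model are all assumed. The largest fold-changes come from the shortest half-life in Q6W, where day 42 is 10.5 half-lives after dosing and the trough in the denominator is close to zero.
- If a visit's injection is delayed or interrupted, a later draw may still be pre-dose.
- The express allowance reaches one on-treatment draw in Q4W and two in Q6W.
- The biomarker issue is the weaker one. Section 3.3.2 places that sample at the Day 1 visit, and Section 4.5.1 allows it to be combined with the parent Week 96 draws. That is permitted, not required, so the route to a late draw stays open but is less likely.

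**Conclusion.** The concern holds. The protocol expressly permits serum PK samples 1 to 7 days after an injection at Q4W Week 48 and Q6W Weeks 48 and 96, and by implication at Q4W Week 96. Section 6.5 would admit them to a summary whose stated objective is trough. The gap rests on the text alone. Its size rests on assumptions and on a statistic the plan does not name: with half-lives of 4 to 14 days and 5% of draws at day 7, the distortion runs from 1.05-fold (geometric mean, Q4W) to 22.5-fold (arithmetic mean, Q6W). It should be fixed because the schedule allows data that do not measure the objective and the analysis would not detect them. It is not critical: the PK objective is observational, the analysis is descriptive, and no primary safety conclusion depends on it.

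**What to change.** 1. In the notes to Appendix 1 Tables 1 and 3, require serum PK and Day 1 biomarker plasma to be drawn before that visit's injection, on the same day or up to 7 days earlier. Align Table 2 footnote d. This follows the rule Appendix 16 already applies to aqueous samples.
2. In Section 6.5, summarize as trough only samples drawn before the visit's injection, using actual time since the last dose, and state the range of days accepted as trough for each schedule. Name the summary statistic. List samples drawn after the visit's injection separately.

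The text is short: one sentence in two notes, one footnote and one analysis rule. The Appendix 1 change is a protocol amendment and goes through the approvals in Section 9.6, so it is best bundled with the next one. The Section 6.5 rule alone would protect the trough summary, but it would not stop off-target samples from being collected. The downside is that a sample missed before the injection cannot be recovered as a trough, so a few values will be lost.
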